18.0 Data Management and Confidentiality

18.1 Data Collection

Full build studies are managed by RPCI CRS Data Management for analysis by RPCI Biostatisticians. All electronic case report form (eCRF) data are captured for these studies.

Data management activities are performed using a CTMS system that enables the collection, cleaning and viewing of clinical trial data. CRS data management designs the study-specific database and facilitates development by the Information Technology team. Once the database design is approved by the Investigator, Statistician, and Clinical Research Coordinator, the database is put into production and data entry can begin. Data can be entered and changed only by those with the rights to do so into the eCRFs.

18.2 Maintenance of Study Documents

Essential documents will be retained per RPCI's policy for 6 years from the study termination date. These documents could be retained for a longer period, however, if required by the applicable local regulatory requirements or by an agreement with RPCI.

18.3 Revisions to the Protocol

RPCI may make such changes to the protocol as it deems necessary for safety reasons or as may be required by the U.S. FDA or other regulatory agencies. Revisions will be submitted to the IRB/ERC for written approval before implementation.

18.4 Termination of the Study

It is agreed that, for reasonable cause, either the RPCI Investigators or Merck, may terminate this study, provided a written notice is submitted within the time period provided for in the Clinical Trial Agreement. In addition, RPCI may terminate the study at any time upon immediate notice if it believes termination is necessary for the safety of participants enrolled in the study.

18.5 Confidentiality

Any data, specimens, forms, reports, video recordings, and other records that leave the site will be identified only by a participant identification number (Participant ID, PID) to maintain confidentiality. All records will be kept in a limited access environment. All computer entry and networking programs will be done using PIDs only. Information will not be released without written authorization of the participant

19.0 Statistical Plan

Primary interest is in the Overall Response Rate (ORR) related to sorafenib + pembrolizumab combination therapy in advanced stage HCC patients. The ORR is defined as the proportion of evaluable patients who attain either complete or partial response (by irRECIST) within 6 months of initiating combination therapy. Our working hypothesis is that sorafenib + pembrolizumab will increase the ORR by at least 15 percentage points over the standard of care (where responses are rare ~2-3%).

19.1 Sample Size Determination

Proposed is a one-stage, single arm, unblinded Phase II trial. ORR for patients receiving the standard of care therapy is around 0.05. An exact one-stage design proposed by Kepner and Chang tests the null hypothesis that the proposed treatment has an ORR that is equal to the

Roswell Park Protocol No.: I 35316

standard of care, against an alternative that it is greater. The design has 80% power to detect an ORR of 0.20 or greater with the study treatment, while controlling to 5% the nominal probability of erroneously finding a truly ineffective treatment as worthy of further research (21, 22).

The first 6 patients will comprise the Phase 1b safety lead-in. If ≥ 2 of these patients experience an unexpected, treatment related toxicity of grade ≥ 3 during the first cycle of therapy, the study will be stopped to reevaluate dosing. We anticipate that such limiting toxicities will be observed in ≤ 1 of the first 6 patients. All evaluable patients who receive the Phase 2 dose will be included in the Phase 2 study.

We expect 27 evaluable patients will be enrolled on the trial. If 4 or more of the 27 evaluable patients achieve complete or partial response, the treatment will be deemed effective and considered for further study.

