9.1 Phase Ib/II

The first 6 patients who have completed at least 4 weeks of sorafenib-only treatment and begin the combination therapy (addition of pembrolizumab at a fixed dose of 200 mg Q3W) will comprise the Phase 1b safety lead-in. Patients who withdraw from the study prior to initiation of combination therapy (for reasons other than DLT) will be replaced.

Definition of Dose-Limiting Toxicity: A dose-limiting toxicity will be defined as any \geq grade 3 clinically significant toxicity which is deemed possibly treatment related and occurs within the first cycle of combination therapy. Toxicity will be assessed according to the NCI Common Terminology Criteria for Adverse Events [Version 4.0 \(CTCAE v4.0\)](#).

Patient data for the safety lead-in portion of the study will be discussed and monitored by The Early Phase Clinical Trials committee, which meets on a regular basis per the RPCI Data Safety Monitoring Plan.

After a minimum of 6 have completed at least one cycle of sorafenib + pembrolizumab, the study will be suspended, and the safety/tolerability of the combination will be examined. At that time, the study team will decide what action to take, e.g., continue the study as is, make changes to the study with regard to treatment or dose modifications, or discontinue the study.

- If ≥ 2 of these patients experience an unexpected, treatment related toxicity of grade ≥ 3 during the first cycle of combination therapy, the study will be stopped to reevaluate dosing. We anticipate that such limiting toxicities will be observed in ≤ 1 of the first 6 patients. All evaluable patients who receive the Phase 2 dose of pembrolizumab (200 mg Q3W) will be included in the Phase 2 study.

Once analysis is complete and a safe treatment plan has been established, the Phase II study will commence.

Patients who have toxicity during the first 3 weeks of combination therapy that appears to be attributed to sorafenib will have sorafenib dose reduced to 2 x 200 mg every other day, as was done in the SHARP study(11). We anticipate such dose modifications to be infrequent. Patients will be considered evaluable if they receive more than 75% of prescribed sorafenib dosing during

Roswell Park Protocol No.: I 35316

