the first 3 weeks of combination therapy (a medication diary will be provided during this time to monitor participant compliance: see Appendix F). All toxicities will be assessed upon completion of the first 6 evaluable patients to see if any higher than anticipated occurrence of sorafenib toxicity is seen due to the addition of pembrolizumab.

The goal of the study is to evaluate efficacy of the combination therapy, therefore patients who are removed from the study prior to receiving the soraf+pembro combination treatment will be replaced. This includes replacing patients who do not tolerate sorafenib alone, as administered in the 1st 4 - 6 weeks of the treatment regimen. In addition, the following patients will be replaced:

- Patient withdraws consent
- Withdrawal from study due to toxicity,
- Withdrawal from study due to liver failure
- Patients who withdraw before the Week 12 (± 1 week) response assessment (for reasons other than progression)

Patients who withdraw due to disease progression prior to the Week 12 (± 1 week) response assessment of the combination therapy will not be replaced and will be counted as non-responders in the response rate calculations.

Patients who complete the 4-6 week initial treatment with sorafenib alone, and withdraw from the study after being treated with the combination therapy will not be replaced and will be counted as non-responders in the response rate calculations.

Patients will receive sorafenib + pembrolizumab until progression. If a patient discontinues either agent due to toxicity, they will still be able to stay on study until progression. Clinical benefit will be considered when making decision to stop therapy as radiographic reflection of true failure of this combination is still unknown.

Disease assessment (imaging) will be done every 6 weeks from the start of C1D1 combination therapy, with a confirmatory assessment no less than 6 weeks after an irPR or irCR or irPD. Therapy will be continued until the confirmatory scan, even if progression is noted on the Week 12 scan. After the 12-week scan disease assessment will be done every 9 weeks (± 1 week). Note: Timing for assessing ORR in patients on immunotherapies is not clear. Disease stability is the commonly seen response to sorafenib alone. Allowing continuation until the confirmatory scan at Week 18, even if progression is seen, allows us to assess the true response to this novel combination.

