19.3 Efficacy Analysis

The response rate will be estimated as the binomial proportion of responders among evaluable patients and supported by Jeffreys' 95% confidence interval.

Time to tumor progression (TTP) will be measured from the date of study enrollment to the first observation of progressive disease. Overall survival (OS) will be measured from the date of study enrollment to the time of death from any cause. These variables will be estimated using the Kaplan-Meier method. Statistics describing the time to event distributions will be obtained from Kaplan-Meier methods and Proportional Hazards models. Continuous variables will be summarized with commonly used statistics (mean, standard deviation, median, etc.), with subgroup associations tested using the Wilcoxon Rank Sum test. Categorical variables will be summarized in contingency tables, with associations of interest assessed using Fisher's Exact Test. Given the exploratory nature of this study, all p-values less than 0.05 will be deemed statistically significant. No adjustment will be made to the significance threshold to control for the effects of multiple testing on the overall Type I error rate.

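### Section 19 rests the primary ORR on *evaluable* patients without defining the term, and the only explicit definition, a sorafenib-intake threshold, would exclude patients who are still on study if it were applied to ORR.

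*Combined protocol and SAP*

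**What the plan says.** Section 19.0 defines ORR as a proportion of evaluable patients. Section 19.1 sets the decision rule at 4 or more responses in 27 evaluable patients and says of the lead-in that "All evaluable patients who receive the Phase 2 dose will be included in the Phase 2 study". Section 19.3 repeats the denominator: "The response rate will be estimated as the binomial proportion of responders among evaluable patients". None of these sections says what makes a patient evaluable.

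The one explicit definition is in Section 9.1, headed Phase Ib/II: "Patients will be considered evaluable if they receive more than 75% of prescribed sorafenib dosing during" the first 3 weeks of combination therapy, with intake tracked by a medication diary. The same section also uses the word for entry of lead-in patients to Phase 2, in nearly the words of Section 19.1.

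Section 9.1 then gives separate rules for the response rate, which turn on withdrawal:

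- Patients who withdraw for progression before the Week 12 assessment are not replaced and count as non-responders.
- Patients who withdraw after receiving the combination are not replaced and count as non-responders.
- Patients who withdraw for toxicity, or for any reason other than progression before Week 12, are replaced.

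The section adds: "If a patient discontinues either agent due to toxicity, they will still be able to stay on study until progression".

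**The concern.** The denominator of the primary endpoint depends on a word that the statistical section leaves open. An analyst who looks for its meaning finds the sorafenib-intake rule and no other. That rule suits an assessment of toxicity in the first cycle, where a patient who took little sorafenib says little about the combination. For ORR, it would select patients on something that happens after combination treatment starts and that can reflect intolerance.

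The patients at issue are those who do not withdraw. Someone who took 75% or less of prescribed sorafenib in the first cycle, kept receiving pembrolizumab and was scanned at Weeks 6 and 12 would fail the definition. The non-responder rules cover withdrawals, so they do not settle where this patient belongs.

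The result would be a response rate among patients who managed sorafenib early in the combination, compared with a fixed standard-of-care rate. If early intolerance goes with a poorer outcome, the selection favours a positive result. In an open-label single-arm trial, it also matters that the denominator be fixed before responses are known.

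**Working it through.** **1. The plan's own figures.** The inputs are all from Section 19.1:

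- null rate: "ORR for patients receiving the standard of care therapy is around 0.05"
- power: "The design has 80% power to detect an ORR of 0.20 or greater with the study treatment"
- type I error: "controlling to 5% the nominal probability of erroneously finding a truly ineffective treatment"
- direction: one-sided, "against an alternative that it is greater"
- rule: at least 4 responses in 27 evaluable patients

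With X binomial(27, p), the exact tail probabilities are:

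- Type I error: P(X ≥ 4 | p = 0.05) = 0.0437.
- Power: P(X ≥ 4 | p = 0.20) = 0.8177. With 26 patients it would be 0.793.

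The stated design reproduces.

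**2. How low intake must be to fail the 75% rule.** Twice-daily dosing for 21 days is 42 doses, and 75% of 42 is 31.5, so at least 32 doses are needed. Six full missed days leave 30/42 = 71.4%, which fails.

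*Prescribed* is not defined. If it means the starting dose, the reduction described in Section 9.1 (2 × 200 mg every other day, an average of 200 mg/day) can also cause failure. For a patient starting at 800 mg/day who is reduced after d days, intake is 800d + 200(21 − d). This is at or below 0.75 × 16,800 = 12,600 when d ≤ 14. If *prescribed* means the dose as reduced or held, fewer patients fail.

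**3. Effect on type I error if the rule were applied to ORR.** Let f be the share of combination-treated patients who fail the 75% rule, and suppose they are replaced until 27 are evaluable. Hold the true ORR in all treated patients at 0.05.

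If the excluded patients respond at a fraction k of the rate of the others, then 0.05 = (1 − f)·p + f·k·p. The rate among evaluable patients is therefore p = 0.05/(1 − f(1 − k)), and the error is P(X ≥ 4 | 27, p). The documents give no value for f or k, so the values below are assumptions.

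| f | p if none respond (k = 0) | Type I error | p if half the rate (k = 0.5) | Type I error |
|---|---|---|---|---|
| 0 | 0.0500 | 4.4% | 0.0500 | 4.4% |
| 5% | 0.0526 | 5.1% | 0.0513 | 4.7% |
| 10% | 0.0556 | 6.0% | 0.0526 | 5.1% |
| 20% | 0.0625 | 8.5% | 0.0556 | 6.0% |

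**4. If the rule removed lead-in patients only.** With 1, 2 or 3 non-responders dropped and replaced, the error is at most P(X ≥ 4 | n, 0.05) with n = 28, 29 or 30. That is 4.9%, 5.5% or 6.1%.

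**5. If excluded patients were not replaced.** Power at 0.20 with the threshold of 4 would be 79.3%, 76.6% or 73.6% with 26, 25 or 24 evaluable patients.

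**6. Consistency with the response-rate rules.** Take a patient who progresses and withdraws in the first cycle after taking 75% or less of prescribed sorafenib. Under the intake rule this patient is not evaluable and leaves the denominator. Under the withdrawal rule in the same section the patient stays in it as a non-responder. Both cannot define the ORR set.

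**The case against.** A reader might infer that patients who cannot take sorafenib do drop out of the primary denominator. The documents do not establish that, for four reasons:

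- **Context.** The 75% sentence follows text on toxicity in the first 3 weeks and comes just before a sentence on assessing toxicities in the first 6 evaluable patients, a use that Section 10.2 repeats. Section 4.0 uses a qualified phrase, evaluable for the primary endpoint, which suggests that more than one kind of evaluability was in mind.
- **Separate response-rate rules.** The paragraph on efficacy in Section 9.1 decides who is replaced and who is a non-responder without mentioning sorafenib intake. The clash in step 6 is itself some evidence that the 75% rule was not meant to define the ORR set.
- **Compliance rather than tolerance.** The threshold concerns prescribed dosing and is tied to a compliance diary that asks for changed doses to be recorded. If a held or reduced dose counts as prescribed, a patient interrupted for toxicity need not fail.
- **Size.** Patients have 4 to 6 weeks of sorafenib alone and must be stable for at least a week before pembrolizumab. Those who do not tolerate sorafenib alone are replaced, and later modifications are expected to be infrequent. The assumption of no responses among excluded patients is the extreme case, and the rule could also discard a genuine responder.

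All four stand as reasons not to assert that bias is present. They do not remove the ambiguity. Sections 9.1 and 19.1 also use *evaluable* for entry to Phase 2, no sentence restricts the 75% rule to toxicity, and if it is so restricted, the ORR has no stated definition of *evaluable*.

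**Conclusion.** The point holds as an undefined primary denominator, with one available reading that would be wrong for ORR. It is not a demonstrated biased analysis. If the 75% rule were applied to ORR, it would exclude on-study patients on a post-treatment event and contradict the non-responder rules in Section 9.1.

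The size cannot be fixed from the documents. At 5% to 20% excluded and replaced, type I error would be 5.1% to 8.5% if none of the excluded respond, and 4.7% to 6.0% if they respond at half the rate of the others, against 4.4% as designed. The smaller shares fit better with the expectation that modifications are infrequent. Even so, the 5% limit is passed at 5% excluded in the first case and at 10% in the second. The direction rests on the assumption that excluded patients respond less often than the others.

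The change should be made, because it costs almost nothing and settles the denominator before responses are counted.

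**What to change.** 1. In Section 9.1, state that the 75% sorafenib rule applies only to the lead-in toxicity assessment.
2. In Sections 19.0, 19.1 and 19.3, define the ORR set without regard to sorafenib intake: all patients who received at least one dose of pembrolizumab in combination, with those lacking a response assessment counted as non-responders. Being still on study should not be a condition of the set. That too is a post-treatment criterion, and it would omit withdrawals that Section 9.1 counts as non-responders.
3. Reconcile the replacement and non-responder rules in Section 9.1 with this set. At present a patient who withdraws for toxicity after starting the combination is both replaced and counted as a non-responder.
4. Count the 27 on this set, so that the rule of 4 keeps its 4.4% error. Its 81.8% power then refers to a true ORR of 20% in the same set.
5. Report ORR in the more-than-75% subset as a sensitivity analysis.

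The cost is a few sentences of text, with no new data and no change to the 27 or to the threshold of 4. The reported ORR may be slightly lower.

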19.2 Demographics and Baseline Characteristics

Descriptive statistics (as appropriate: n, percent, mean, median, min and max) will be used to summarize demographic and baseline characteristics.

19.3 Efficacy Analysis

The response rate will be estimated as the binomial proportion of responders among evaluable patients and supported by Jeffreys' 95% confidence interval.

Time to tumor progression (TTP) will be measured from the date of study enrollment to the first observation of progressive disease. Overall survival (OS) will be measured from the date of study enrollment to the time of death from any cause. These variables will be estimated using the Kaplan-Meier method. Statistics describing the time to event distributions will be obtained from Kaplan-Meier methods and Proportional Hazards models. Continuous variables will be summarized with commonly used statistics (mean, standard deviation, median, etc.), with subgroup associations tested using the Wilcoxon Rank Sum test. Categorical variables will be summarized in contingency tables, with associations of interest assessed using Fisher's Exact Test. Given the exploratory nature of this study, all p-values less than 0.05 will be deemed statistically significant. No adjustment will be made to the significance threshold to control for the effects of multiple testing on the overall Type I error rate.

19.4 Correlative Data Analysis

Measurements for several immune parameters will be obtained before and after treatment. The effect of treatment will quantified as the post/pre-treatment mean ratio of the (potentially log transformed) expression measurements. Primary and derived immune marker expression measurements will be summarized with common descriptive statistics (mean / standard deviation). Associations between the paired pre- and post-measurements will be described with scatterplots and dot plots. The null hypothesis of no difference in the paired pre- and post-treatment measurements was assessed using permutation paired t-tests.

In previous experiments, immune marker expression measurements varied widely, with means between 8.0 and 1,200; the coefficient of variation has been between 0.5 and 1.0. For power calculations, the (original scale) expressions are assumed to have mean (standard deviation) of 100 (100), and within-patient correlation = 0.20. Comparing measurements at two time points, the within-patient effect of therapy on an immune marker can be assessed using a permutation paired t-test. A paired t-test with a two-sided significance threshold of 0.05 has 80% power to

Roswell Park Protocol No.: I 35316

detect a fold-change of at least 1.76 in the post/pre geometric means.

All data analyses were generated using SAS/STAT software, Version 9.4. Copyright 2012, SAS Institute Inc. SAS is a registered trademark of SAS Institute Inc., Cary, NC, USA.

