1.3 Exploratory Objectives

- To obtain data on changes in immune cell function and in the tumor microenvironment pre- and post-treatment to screen for potential biomarkers that may be able to predict clinical benefit.
- All patients will be followed for survival.

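### For a log-transformed immune marker, Section 19.4's effect rule taken literally is a ratio of mean logs, not the geometric-mean fold-change that the same section powers

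*Combined protocol and SAP*

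**What the plan says.** Section 19.4 (Correlative Data Analysis) gives the plan's only definition of the marker effect: "The effect of treatment will quantified as the post/pre-treatment mean ratio of the (potentially log transformed) expression measurements". Logging is optional, and the section does not say which markers will be logged. It mentions neither a difference of logs nor a back-transformation.

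On testing, the section says: "The null hypothesis of no difference in the paired pre- and post-treatment measurements was assessed using permutation paired t-tests".

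On power, it reports that in earlier experiments marker levels varied widely, "with means between 8.0 and 1,200; the coefficient of variation has been between 0.5 and 1.0". For the calculation, "the (original scale) expressions are assumed to have mean (standard deviation) of 100 (100), and within-patient correlation = 0.20". A paired t-test at two-sided 0.05 is then said to have 80% power to "detect a fold-change of at least 1.76 in the post/pre geometric means". Section 19.4 does not give the number of pairs. Section 19.1 says: "We expect 27 evaluable patients will be enrolled on the trial".

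The analysis serves an exploratory objective in Section 1.3: "To obtain data on changes in immune cell function and in the tumor microenvironment pre- and post-treatment to screen for potential biomarkers".

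**The concern.** On the log scale a treatment effect is a difference. Exponentiating the mean difference gives the ratio of geometric means, which is a fold-change. Dividing one log-scale mean by another gives a number with no such meaning. Changing the units adds the same constant to both means, and that alters their ratio.

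Section 19.4 therefore contains two effect measures for a logged marker: the ratio of mean logs that its definition implies, and the geometric-mean ratio that its power sentence uses. If an analyst followed the definition literally, the same biological change would get a different effect size for each marker level and unit. No reported value could be set against the 1.76 target. Because the aim is to screen several markers, a reader will naturally compare effects across them.

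**Working it through.** **Inputs.** From Section 19.4: mean 100, SD 100 (so CV = 1), within-patient correlation 0.20 on the original scale, two-sided alpha 0.05, power 80%, marker means 8 to 1,200, CV 0.5 to 1.0. From Section 19.1: n = 27, assumed to be the number of pairs. Lognormal data with the same CV before and after treatment are also assumed.

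**1. Reproduce the plan's 1.76.**
- Log-scale variance: ln(1 + CV²) = ln 2 = 0.6931.
- Log-scale covariance: ln(1 + 0.20 × CV²) = ln 1.2 = 0.1823, so the log-scale correlation is 0.1823/0.6931 = 0.263.
- SD of the within-patient log difference: √[2 × (0.6931 − 0.1823)] = 1.0108.
- Standard error with 27 pairs: 1.0108/√27 = 0.1945.
- A 1.76-fold change is ln 1.76 = 0.5653 on the log scale, so the noncentrality is 0.5653/0.1945 = 2.91.
- The noncentral t distribution with 26 degrees of freedom gives power of 79.9% at 1.76, and a detectable ratio of 1.7615 at 80% power.

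The plan's figure is reproduced as the exponential of a mean log difference, that is, a ratio of geometric means. If the correlation of 0.20 is applied directly on the log scale, the detectable ratio is 1.80 (noncentral t) or 1.76 (normal approximation). These too are ratios of geometric means.

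**2. Apply the definition literally to a logged marker.** For lognormal data the mean log before treatment is m = ln(mean) − ½ ln(1 + CV²). After a true 1.76-fold rise it is m + 0.5653. The literal effect is (m + 0.5653)/m.

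| Marker mean | CV | Mean log before | Mean log after | Literal ratio |
|---|---|---|---|---|
| 8 | 1.0 | 1.7329 | 2.2982 | 1.33 |
| 100 | 1.0 | 4.2586 | 4.8239 | 1.13 |
| 1,200 | 1.0 | 6.7435 | 7.3088 | 1.08 |
| 8 | 0.5 | 1.9679 | 2.5332 | 1.29 |
| 100 | 0.5 | 4.4936 | 5.0589 | 1.13 |
| 1,200 | 0.5 | 6.9785 | 7.5438 | 1.08 |

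With CV = 1, a rise of 76% would thus appear as 33%, 13% or 8%, depending only on the marker level.

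**3. Units and log base.** The same rows show the dependence on units. Restating a marker of mean 8 in units 12.5 times smaller gives a mean of 100, and the literal ratio moves from 1.33 to 1.13 with no change in biology. The log base does not matter: at mean 100 and CV 1 the ratio is 1.1327 with log2 and with log10.

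**4. The valid alternatives.** In 20,000 simulated trials of 27 pairs at each of the three means (CV 1, true rise 1.76), the median geometric-mean ratio was 1.76 and the median ratio of arithmetic means was 1.76 to 1.77. The median ratio of mean logs was 1.33, 1.13 and 1.08.

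**The case against.** The strongest reply is that the power sentence in the same section shows what was meant. The 1.76 is stated as a ratio of geometric means and reproduces as one, so the definition may be loose shorthand: arithmetic-mean ratios for unlogged markers, geometric-mean ratios for logged ones. This is a likely reading, and it shows which wording to adopt. It does not make the present sentence correct, because nothing in the section tells the analyst to difference the logs and back-transform.

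Three stronger conclusions are tempting, and the documents do not support them.

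- *A reader might infer that the reported marker effects will be wrong.* Logging is only a possibility under the plan, and the unlogged ratio of means is a sound fold-change. Error follows only if a marker is logged and the sentence is then applied literally.
- *A reader might infer that the direction of an effect could reverse.* This can happen when levels fall below 1. A marker of mean 8 restated in units 100 times larger (mean 0.08, CV 1) gives −2.3070/−2.8723 = 0.80 for the same rise. Sections 2.2 and 14.0 do speak of frequencies and percentages of PD-1+ cells. But the documents nowhere say that a marker will be stored as a proportion, and the quoted means are 8 to 1,200. In that range the expected log means are positive and the literal ratio is attenuated but keeps its direction.
- *A reader might infer that the tests or the power are compromised.* The permutation paired t-test works on the paired measurements and does not use the ratio, and the 1.76 stands.

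It is also fair to say that the analysis is exploratory and that the planned means, SDs and plots would help a careful reader to notice an odd ratio.

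**Conclusion.** Wrong as written, of minor severity. The defect is confined to the descriptive effect size for log-transformed markers in an exploratory analysis. Over the plan's range of marker means, the literal rule would show a true 1.76-fold rise as 1.33 down to 1.08 (CV 1) or 1.29 down to 1.08 (CV 0.5), so neither comparison across markers nor comparison with the 1.76 target would be valid.

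These figures rest on lognormal data and an equal CV before and after treatment. The reproduction of 1.76 also rests on 27 pairs, which Section 19.4 does not state. That the ratio of mean logs is not a fold-change and depends on units needs none of these assumptions. The response rate, time to progression, sample size and decision rule are untouched.

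**What to change.** Replace the defining sentence in Section 19.4 with:

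> For log-transformed markers the effect is the mean within-patient difference in logs (post minus pre), exponentiated and reported as the post/pre ratio of geometric means with a 95% CI; for untransformed markers it is the post/pre ratio of arithmetic means.

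Use the ratio, not a difference of arithmetic means, for untransformed markers, since a difference would bring back dependence on units. A short clause stating which markers will be logged would settle which half of the rule applies to each.

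The cost is one sentence. No new data are needed, and the power statement stays as it is: under this definition a true 1.76-fold change has the value 1.76 at every marker level.
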